2. OVERALL SYNOPSIS OF THE CLINICAL INVESTIGATION

Clinical investigation title:	Performance Comparison between Masimo W1™ and Apple Watch Series 8
Study objective(s):	
Primary Objective: Evaluate the performance of Masimo W1™ against FDA cleared hospital grade pulse oximetry technology under desaturation conditions.
 
Secondary Objective: Compare the performance of Masimo W1™ and Apple Watch Series 8 against FDA cleared hospital grade pulse oximetry technology under desaturation conditions.

Study device(s):	Masimo W1™ Apple Watch Series 8 Masimo RD SET Adt
Number of subjects:	Up to 40 subjects.
Inclusion criteria:	
 Subject is 18 to 55 years of age. Subject is American Society Anesthesiologist status 1 (ASA I) Subject has a BMI between 18 and 35. Subject is able to read and communicate in English and understands the study and the risks involved.
Exclusion criteria:	
 Subject is currently taking any medications which in the opinion of the principal investigator would not be suitable for participation in the study. Subject is wearing nail polish that cannot be removed, gel nails, and/or acrylic nails that can interfere with study device's placement. Participants with conditions or skin abnormalities at or around site of sensor placement that could affect the placement on the sensor or prevent monitoring of physiological parameters during the study, such as psoriasis, eczema, angioma, scar tissue, burn, fungal infection, substantial skin breakdown. Subject has participated in an investigational drug study within one month prior to the start of the study. Subject has failed the Allen's Test to confirm patency of the collateral artery. Subject is female with a positive pregnancy test, or is female and is unwilling to use effective birth control between the time of screening and study termination. Subject has a positive urine cotinine or drug test. Subject has a reported allergy to Lidocaine. Subject has clinically significant anemia or other hemoglobinopathy. Subject has a room air saturation of less than 95% by pulse oximetry. Subject has a clinically significant abnormal EKG. Subject has a clinically significant abnormal pulmonary function test via spirometry. Subject is intolerant to a breathing mask apparatus. Subject has a COHb greater than 3%, or MetHb greater than 2% verified by laboratory co-oximeter. Subject has another condition, which in the opinion of the principal investigator would not be suitable for participation in the study. Subject is unwilling or unable to provide informed consent or comply with the study procedures.
Duration of the clinical investigation:	Expected duration of study enrollment is 1 to 3 months. Subject participation in the study will be approximately 6 hours (approx. 2 hours for the screening phase and 4 hours for the data collection phase)

Study endpoint(s):	Primary endpoint: Performance of oxygen saturation (SpO ₂) measurements reported by Masimo W1™. Secondary endpoint: Performance of oxygen saturation (SpO ₂) measurements reported by Masimo W1™ watch and Apple watch series 8.
--------------------	---

3. IDENTIFICATION AND DESCRIPTION OF THE INVESTIGATIONAL DEVICE

Masimo Corporation is the developer of noninvasive technologies for the measurement and monitoring of physiological variables, such as arterial oxygen saturation (SpO₂), total hemoglobin concentration (SpHb), carboxyhemoglobin concentration (SpCO), methemoglobin concentration (SpMet), and other physiological variables to improve patient outcomes and reduce cost of care.

The Masimo W1™ is a watch that provides spot-check ECG measurements and continuous measurements of functional oxygen saturation of arterial hemoglobin (SpO₂), pulse rate (PR), and respiration rate from the pleth (RRp®). The watch has a touchscreen display, a rechargeable battery, and Bluetooth® connectivity to pair to a smartphone App.

Figure 1: Masimo W1™

Additional study devices that will be used in this study include the Apple Series 8 watch, the Masimo Rad-97 Pulse CO-Oximeter and the Masimo RD SET Adt sensor. The Rad-97 and Masimo RD SET are indicated for the continuous non-invasive monitoring of functional oxygen saturation (SpO₂), pulse rate (PR), respiratory rate (RRa), and Pleth Variability index (PVi) for adult populations.

The Apple Series 8 watch will be connected to an iPhone, results from the spot check measurements on the Apple Watch will also be manually recorded in the comments portion of a data collection software on a laptop. The Rad-97/RD SET pulse oximeter will be connected to a data collection software on a laptop.

Figure 2: Masimo Rad-97 Pulse CO-Oximeter

Figure 3: Masimo RD SET Adt Sensor

4. JUSTIFICATION FOR THE DESIGN OF THE CLINICAL INVESTIGATION

This study is designed to compare the performance of Masimo W1™ and Apple Watch Series 8 to FDA-cleared RD SET Adt for SpO2 as the subjects undergo a controlled desaturation protocol. This type of study design is required to evaluate the performance of pulse oximeters based upon the ISO 80601-2-61 standard which is also adopted and referenced by the FDA.

5. BENEFITS AND RISKS OF THE INVESTIGATIONAL DEVICE, CLINICAL PROCEDURE, AND CLINICAL INVESTIGATION**5.1. Anticipated Clinical Benefits**

There will be no benefit to the subject. Benefits would be to society as a whole. Equivalence of the accuracy of this pulse oximetry device could enable users to monitor and identify potentially life-threatening conditions more appropriately.

5.2. Anticipated Adverse Device Effects

See [List of Anticipated Adverse Effects](#) under section 17.2.

5.3. Risks/Discomforts Associated with Participation in the Clinical Investigation

The following risks/discomforts associated with study procedures are anticipated adverse events. These anticipated adverse events are expected to be temporary.

All adverse events will be documented and reported following procedures outlined in this document.

Risks Associated with the Device

The noninvasive devices used in this study are similar in technology and design to some commercially available pulse oximeters and other noninvasive devices and hence have the same risks. Pulse oximeters and other noninvasive devices are commonly used and are considered to be minimal risk.

There is a small risk of damage to the subject's wrist(s) and/or finger(s), from the device, including temporary skin irritation, skin inflammation, itching skin, or discomfort associated with exposure to the sensor, as well as potential temporary mechanical irritation or discomfort.

If there are any cuts and/or abrasions near the sensor application site, sensors may not be placed on the particular wrist to avoid any discomfort for the subject.

Risks of Colorimeter

The light is cold to the touch and does not pose any burn risk to the skin.

Risks of Blood Pressure Cuff

The reported risks associated with non-invasive blood pressure (NIBP) cuff measurement include discomfort upon inflation of the cuff, possible bruising, rash (small red or purple spots on the skin, caused by a minor bleed from broken capillary blood vessels), and discoloration of the skin beneath the cuff. Risks may also include nerve injuries (impaired movement, sensation, or function), skin tear, and compartment syndrome.

Risks Associated with Venous Blood Draw Risks

Discomfort is generally associated with needle puncture. The most common complications associated with blood draws are hematomas or bruising.

There is also a possible risk of infection, tendon or tissue damage, damage to the blood vessel and surrounding nerves, inadvertent arterial puncture, and/or loss of feeling in the hand and/or arm.

Other anticipated adverse events that may occur, include but are not limited to vasovagal syncope (fainting), lightheadedness, feeling flush/warm, feeling pain, feeling nauseated, throwing up, seizures, sudden drop in blood pressure/sudden increase in blood

pressure, sudden drop in heart rate/sudden increase in heart rate, tingling sensation of face, arms and/or legs, sweating, and/or mouth dryness.

Risks Associated with Lidocaine Injection

Injection of lidocaine may be discomforting and can feel like a slight pinch along with a warm/burning sensation.

Other anticipated adverse events that may occur, include but are not limited to pain, flushing or redness of the skin, itching skin, small red or purple spots on the skin, unusually warm skin, bruising, bleeding at the application site, swelling, feeling nauseated, dizziness, low blood pressure, and/or tremors.

Although not common, it is also possible to have an allergic reaction to injectable lidocaine (e.g., seizures). Subjects should not take part in this study if they are allergic to lidocaine injection or other types of numbing medicine. Subjects are instructed to tell the study staff right away if they experience hives; difficulty breathing; or swelling of their face, lips, tongue or throat.

Risks Associated with Low Oxygen Administration (Desaturation)

Risks associated with hypoxia include dizziness, shortness of breath, drowsiness, or headache. If or when this occurs, the study can be stopped.

There is an extremely small risk of loss of consciousness or death from lack of oxygen. The study shall be stopped by the subject or clinical staff long before this can occur.

Breathing a hypoxic (reduced oxygen) mixture has potential risks that include damage to vital organs such as the brain, liver, kidney and/or heart. Note that several studies have been done with low oxygen using generally healthy subjects without any serious or permanent damage to any of the major organs.

Other anticipated adverse events that may occur, include but are not limited to: vasovagal syncope (fainting), lightheadedness, chest discomfort (e.g. chest tightness, chest pain), feeling flush/warm, feeling of anxiety, feeling nauseated, throwing up, seizures, sudden drop in blood pressure/sudden increase in blood pressure, sudden drop in heart rate/sudden increase in heart rate, irregular heart rate (PAC, PVC, ECG abnormalities, etc.), tingling sensation of face, arms and/or legs, sweating, mouth dryness, feeling claustrophobic or anxiousness from wearing a mouthpiece and/or mask.

Risks Associated with Carbon Dioxide Administration

Risks associated with carbon dioxide administration include dizziness, shortness of breath, drowsiness, or headache. If or when this occurs, the study can be stopped.

Other anticipated adverse events that may occur, include but are not limited to tingling, prickling sensations (“pins and needles” feeling), restlessness, sudden drop in blood pressure/sudden increase in blood pressure, sudden drop-in heart rate/sudden increase in heart rate, irregular heart rate (PAC, PVC, ECG abnormalities, etc.), sweating, and/or feeling claustrophobic or anxiousness from wearing a mouthpiece and/or mask.

Risks Associated with Mask Application

A mask may be applied to the subject's face using an adhesive dressing or using straps. Risks associated with mask adherence include skin irritation, redness of the skin, itchiness, tingling sensation, rash, changes in skin color, and/or headache. It is expected that some people may experience feelings of claustrophobia or anxiousness from wearing a mask.

It is expected that some people may experience increased pressure around the area of the mask, this is expected to be temporary and resolve once mask is removed.

Subjects should not take part in this study if they are allergic to adhesives. Subjects' answers on the health questionnaire will help the medical staff decide if they can safely participate in this study; subjects are encouraged to let the study staff know if they have any concerns.

Risks Associated with Shaving

Subjects may be asked to shave the area of sensor and/or mask application to allow the sensors and/or mask to stick to the skin.

Risks associated with shaving include cuts and/or abrasions, bleeding, infection, razor burn, rash, itching skin, flushing or redness of the skin, unusually warm skin, skin inflammation, skin irritation, ingrown hairs, and/or inflamed hair follicles. Each of these discomforts and side effects are temporary and should fade over time. Some of these symptoms may last up to several days after shaving.

If there are any cuts and/or abrasions near the area of sensor and/or mask application, certain types of sensors or masks may not be placed on the particular location to avoid any discomfort for the subject.

Within the consent form, subjects will agree to have sensor adhesion sites shaved or not. Subjects can stop these measures at any time if they feel uncomfortable.

Risks Associated with Warming

Changes in temperature may cause temporary changes in heart rate, or premature ventricular contractions (PVC). The most common discomforts associated with warming may include sweating and/or may cause the subject to feel tired. In rare instances skin burns may occur when using heating/warming pads, in the case that this may occur, the warming pad will be removed and our medical staff will determine proper course of action depending on the severity of the burn. Other discomforts may include lightheadedness, dizziness, nausea, clamminess, and/or feeling claustrophobic.

Reproductive Risks

Low oxygen levels may affect normal development of a fetus, so women who are pregnant or planning a pregnancy are not allowed to participate in this research study.

6. OBJECTIVES OF THE CLINICAL INVESTIGATION

Primary Objective: Evaluate the performance of Masimo W1™ against FDA-cleared hospital grade pulse oximetry technology under desaturation conditions.

Secondary Objective: Compare the performance of Masimo W1™ and Apple Watch Series 8 against FDA-cleared hospital grade pulse oximetry technology under desaturation conditions.

7. DESIGN OF THE CLINICAL INVESTIGATION

7.1. General

Data using the noninvasive devices will be collected from generally healthy male and female volunteers undergoing a desaturation procedure. Study subjects of differing levels of skin pigmentation will be enrolled in the study.

This is a nonrandomized single arm study wherein all subjects are enrolled into the experimental arm and receive Masimo W1™ and Apple Watch Series 8 on their wrist(s) and FDA-cleared RD SET Adt on at least one finger. Desaturation will be conducted by reducing the concentration of oxygen the study subject breathes in a controlled manner to obtain noninvasive oxygen saturation readings, SpO₂, at various levels.

SpO₂ performance will be calculated using Accuracy Root Mean Square (A_{RMS}) analysis of the SpO₂ values and the reference FDA-cleared RD SET Adt values.

Outcome Measure:

SpO₂ equivalence will be determined by calculating the A_{RMS} value through the comparison of the noninvasive oxygen saturation measurement (SpO₂) to the noninvasive oxygen saturation measurement (SpO₂) value obtained from the FDA-cleared hospital grade pulse oximetry technology.

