7.4. Study Devices and Comparators

Study Devices and Technologies

- Masimo W1™ – Test
- Apple Watch Series 8 – Test
- RD SET® Adt - Control

FDA-Cleared Safety Equipment

- Capnostream 20
- Nefin bmeye
- ECG Module

Research Equipment (as needed)

- Masimo Pulse Co-Oximeter (Rad-97 or comparable)
- Data Collection Research Equipment (e.g. [REDACTED] Lab Chart, smart phone with data collection application or comparable)
- Colorimeter (e.g., Delfin SkinColorCatch or comparable)
- Warm water bottle, heating pad or Comparable
- [REDACTED]
- Laboratory CO-oximeters/blood analyzers (e.g. Radiometer ABL90 Flex or comparable)

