10.1.3. Accuracy Calculations

Accuracy will be reported as the Bias, Precision and A_{RMS} using the following equations:

$$Bias = \frac{1}{n} \sum_{i=1}^n (Test\ SpO_2 - Reference\ SpO_2)$$

$$Precision = \sqrt{\frac{\sum_{i=1}^n (Test\ SpO_2 - Reference\ SpO_2) - Bias)^2}{n}}$$

$$A_{RMS} = \sqrt{\frac{\sum_{i=1}^n (Test\ SpO_2 - Reference\ SpO_2)^2}{n}}$$

The precision and A_{RMS} values will be adjusted to account for repeated measurements on each subject.

10.1.4. No Read Rate for Spot Checks:

$$No\ Read\ Rate = (Nf / N_{spotcheck}) \times 100\ (%)$$

Where, Nf = Number of Spot Checks without Valid SpO_2

$N_{spotcheck}$ = Number of All Spot Checks using Apple Watch

No Read Rate will be calculated for overall and for each no-motion and motion spot check subgroup.

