15. STATEMENTS OF COMPLIANCE

This document is a clinical investigational plan for a human research study sponsored by Masimo Corporation. The study will be conducted in accordance with the ethical principles that have their origin in the Declaration of Helsinki. By participating in the study, the Investigator agrees to adhere to all stipulations of this protocol, the conditions of the Institutional Review Board (IRB) or Research Ethics Committee approval, federal and local regulatory requirements, 21 CFR 812, ISO-14155, International Conference on Harmonization Good Clinical Practice (ICH GCP) guidance.

The protocol, informed consent form(s), recruitment materials, and all participant materials will be submitted to the Institutional Review Board (IRB) for review and approval. Approval of both the protocol and the consent form must be obtained before any participant is enrolled. Any amendment to the protocol will require review and approval by the IRB before the changes are implemented to the study.

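### A_RMS against RD SET Adt measures agreement with a same-manufacturer pulse oximeter, so a lower value for W1 would not by itself show that W1 is the more accurate watch

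*Combined protocol and SAP*

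**What the plan says.** - **Reference.** Section 7.1 calculates A_RMS from the test SpO2 and "the reference FDA-cleared RD SET Adt values". Its outcome-measure paragraph bases SpO2 equivalence on that A_RMS, comparing one non-invasive SpO2 with the "value obtained from the FDA-cleared hospital grade pulse oximetry technology".
- **Manufacturer.** Section 3 lists as further study equipment "the Masimo Rad-97 Pulse CO-Oximeter and the Masimo RD SET Adt sensor". W1 is also a Masimo device, and section 15 describes a "human research study sponsored by Masimo Corporation".
- **Roles.** Section 7.4 lists both watches as test devices and "RD SET® Adt - Control".
- **Label.** Section 10.1.3 says "Accuracy will be reported as the Bias, Precision and A_{RMS} using the following equations". Each equation is a function of test minus reference. The only adjustment named is for repeated measurements within a subject.
- **Use.** The secondary objective (sections 2 and 6) compares W1 and the Apple Watch against this same reference.
- **Blood reference.** None is described. The co-oximeter in section 8.3.2 is for COHb and MetHb in a venous screening sample, and the optional line in section 8.4.1 is venous.

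The documents state no error for RD SET Adt and no correlation between its errors and those of either watch.

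**The concern.** A pulse oximeter used as reference has its own error, and that error enters every test-minus-reference difference. If a test device's errors are independent of the reference's, A_RMS is inflated. If they move together, part of the error cancels and A_RMS falls, possibly below the device's true error.

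W1 and RD SET Adt come from one manufacturer, so it is reasonable to allow that W1 shares more error with the reference than the Apple Watch does. A lower A_RMS for W1 could then arise wholly or partly from the choice of reference. Under a heading of accuracy, a report could say that one watch is more accurate when the data show only which agrees more closely with RD SET Adt.

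**Working it through.** The plan states no A_RMS limit, margin, reference error or correlation, so there is no figure of its own to reproduce. The check applies the plan's A_RMS formula to a simple error model.

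**Model.** Test = true saturation + test error (bias b_T, SD s). Reference = true saturation + reference error (bias b_R, SD r). The two errors have correlation ρ. Then

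- expected A_RMS² against the reference = (b_T − b_R)² + s² + r² − 2ρsr
- A_RMS² against true saturation = b_T² + s²

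The two differ unless the reference terms happen to cancel.

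**Inputs.** All are assumed, in SpO2 points: s = 2.0 for both watches, so the two are equally accurate; zero bias; r = 1.0 or 1.5; ρ = 0, 0.25 or 0.5.

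| r | ρ = 0 | ρ = 0.25 | ρ = 0.5 |
|---|---|---|---|
| 1.0 | √(4 + 1) = 2.24 | √(5 − 1) = 2.00 | √(5 − 2) = 1.73 |
| 1.5 | √(4 + 2.25) = 2.50 | √(6.25 − 1.5) = 2.18 | √(6.25 − 3) = 1.80 |

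**Each watch alone.** True A_RMS is 2.0 in every cell. Independent errors give 2.24 or 2.50, which is too high. The observed value falls below the true one once ρ exceeds r/(2s), which is 0.25 for r = 1.0 and 0.375 for r = 1.5. The direction of the distortion is therefore unknown.

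**Between watches, one at ρ = 0 and the other correlated.**

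- r = 1.0: 2.24 − 2.00 = 0.24 and 2.24 − 1.73 = 0.51 (0.50 before rounding)
- r = 1.5: 2.50 − 2.18 = 0.32 and 2.50 − 1.80 = 0.70

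Equally accurate watches could thus differ by about 0.2 to 0.7 points.

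**Between watches, both correlated.** If both have ρ = 0.5 with r = 1.5, both show 1.80 and the gap is zero. If one has 0.25 and the other 0.5, the gap is 2.18 − 1.80 = 0.38.

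**Can the order reverse?** Let W1 be truly worse (s = 2.5, against 2.0 for the Apple Watch), with r = 1.5, ρ = 0.5 for W1 and 0 for Apple. W1 shows √(6.25 + 2.25 − 3.75) = 2.18 and Apple shows 2.50. At ρ = 0.3 for W1 they tie, since √(8.5 − 2.25) = 2.50. Reversal is possible under such inputs; nothing shows that it is likely.

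**The case against.** The strongest reply is that little is concealed. Both objectives say that performance is judged against a cleared pulse oximeter, section 4 names RD SET Adt, and section 10.1.3 defines every statistic as test minus reference. The word accuracy is also part of the name A_RMS. This stands: the reference is disclosed, and the fault lies in the label and in what may be concluded from it.

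Three stronger readings are tempting, and the documents support none of them.

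- *The Apple Watch shares no error with the reference.* The plan gives no error model for any device. It does not say that W1 and RD SET Adt share an algorithm, nor that the Apple Watch shares nothing with them. Both watches are worn at the wrist and RD SET Adt on a finger, so differences due to site could be common to both watches. Only possible unequal sharing can be claimed.
- *The plan will report equivalence of accuracy.* Section 5.1 does say "Equivalence of the accuracy of this pulse oximetry device could enable users", but as a conditional statement of benefit to society about one device. Section 7.1 speaks of SpO2 equivalence. The reporting label at issue is the one in section 10.1.3.
- *The trial's own data could separate each watch's error from the reference's.* Even with all three sets of pairwise differences, three variances would face six unknowns (three SDs and three correlations). The plan also describes no pairing of W1 with the Apple Watch.

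It is also fair to say that section 10 defines no W1-versus-Apple statistic, test or ranking rule. The secondary objective nevertheless calls for a comparison, and nothing limits how it may be read.

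**Conclusion.** The point holds as a limit on interpretation. Bias, precision and A_RMS under sections 7.1 and 10.1.3 measure agreement with RD SET Adt. Calling them accuracy goes beyond the design, and a lower A_RMS for W1 would not by itself establish better accuracy than the Apple Watch.

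The gap of about 0.2 to 0.7 points is an illustration, not an estimate of bias in this trial. It rests on assumed SDs, zero bias, and correlation in one watch only; it shrinks as the correlations approach each other and vanishes when they are equal. The documents establish the common manufacturer and the non-invasive reference. They do not establish that any tilt exists, or how large it is.

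**What to change.** Keep the reference and the A_RMS formula, and change the wording in three places:

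1. In section 10.1.3, report bias, precision and A_RMS as agreement with RD SET Adt.
2. In section 7.1, state that SpO2 equivalence means agreement with RD SET Adt.
3. With the secondary objective, state that the W1 and Apple Watch results will be compared only as agreement with a reference from the W1 manufacturer, and that no conclusion will be drawn that either watch is more accurate.

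No sensitivity table of implied device errors is proposed, because the data could not identify its entries. The change needs no new procedure, subject or measurement. The cost is a narrower claim for the trial.

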7.2. Investigation Site(s)

7.3. Definition of Completion of the Clinical Investigation

The study will be considered as complete when 20 subjects have been evaluated and a final clinical study report is complete, excluding those who have been withdrawn.

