10. STATISTICAL DESIGN AND ANALYSIS

10.1. Slow Desaturation

10.1.1. Sample Size

10.1.1.1. This study will include at least 10 Dark skin pigmentation subjects based on ISO-80601-2-61.

10.1.1.2. This study will include at least 10 Light skin pigmentation subjects based on ISO-80601-2-61.

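### Section 7.1 promises an equivalence determination from A_RMS, but the plan states no limit, interval or decision rule, so it supports description only

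*Combined protocol and SAP*

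**What the plan says.** Under the outcome measure in 7.1, SpO2 "equivalence will be determined by calculating the A_{RMS} value", comparing the test reading with the reading from the FDA-cleared oximeter. Section 5.1 rests the expected benefit to society on equivalent accuracy of the device.

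The rest of the plan uses weaker language. The primary objective in section 6 is to "Evaluate the performance of Masimo W1™ against FDA-cleared hospital grade pulse oximetry technology" under desaturation, and the synopsis names the primary endpoint simply as performance. Section 10.1.3 states "Accuracy will be reported as the Bias, Precision and A_{RMS", gives three point formulas, and adds: "The precision and A_{RMS} values will be adjusted to account for repeated measurements on each subject". No method, interval or level follows.

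ISO 80601-2-61 appears in three roles: as the basis of the design in section 4 ("evaluate the performance of pulse oximeters based upon the ISO 80601-2-61 standard"), as the basis of the subject counts in 10.1.1 and 10.2.1 (for example "at least 10 Dark skin pigmentation subjects based on ISO-80601-2-61"), and in the bibliography. On size, 7.3 says "The study will be considered as complete when 20 subjects have been evaluated", while 7.5.3 allows up to 40 enrolled.

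**The concern.** To determine equivalence is to reach a yes-or-no conclusion. That needs a value of A_RMS separating yes from no, and a way to allow for sampling error. The plan gives neither, so no A_RMS result could confirm or refute the claim that 7.1 announces. The judgement would be made after the numbers are known, by a sponsor that makes one of the test devices.

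The sample makes this matter. With 20 subjects and repeated readings on each, the information depends on the number of people more than on the number of pairs. An A_RMS that looks comfortably small can come from a device that is materially worse, and a bare point value does not show this.

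**Working it through.** **1. Is there a criterion anywhere?** The passages side by side:

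| Place | What it supplies |
|---|---|
| 7.1 | Equivalence conclusion from A_RMS; no limit |
| 5.1 | Equivalence of accuracy as a benefit; no limit |
| 4, 10.1.1, 10.2.1, bibliography | ISO 80601-2-61 for design and counts; no limit quoted or adopted |
| Synopsis, 6 | Evaluate, compare, performance; no threshold |
| 10.1.2.6 | 2% stability of the reference: a rule for including a pair |
| 10.2.2.4 | 92% reference SpO2: defines a valid fast-desaturation event |
| 10.1.3 | Point formulas; unnamed adjustment; no interval |

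The two percentages that might be taken for accuracy limits are data rules. Section 10 shows no blackout marks and its numbering is unbroken (10.1.1 to 10.1.4, 10.2.1 to 10.2.4).

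**2. The one figure that can be reproduced.** 10 dark + 10 light = 20, which agrees with 7.3. This is a count. No margin, SD, alpha or power is given from which to rebuild an equivalence calculation.

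**3. How much A_RMS moves by sampling (assumed inputs).** Let each error be a normal subject bias plus normal within-subject error. S is the number of subjects, m the pairs per subject, ρ the intraclass correlation and μ the mean bias. Scale the true A_RMS to 1, so that σ² = 1 − μ². For the unadjusted A_RMS:

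Var(A_RMS²) = (1/S) × { (2σ⁴ + 4μ²σ²)/m + [(m−1)/m] × (2ρ²σ⁴ + 4μ²ρσ²) }

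95% half-width of A_RMS ≈ 1.96 × √Var / 2.

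- Narrowest setting (S = 20, m = 40, ρ = 0.25, μ = 0): (1/20) × (2/40 + 0.975 × 0.125) = 0.00859; √ = 0.0927; half-width 9.1%. Simulation: −8.3% to +9.8%.
- Widest setting (S = 20, m = 10, ρ = 0.7, μ = 0.5, σ² = 0.75): (1/20) × (0.1875 + 0.9 × 1.07625) = 0.0578; √ = 0.2404; half-width 23.6%. Simulation: −22.9% to +23.8%.
- With 40 subjects, divide by √2: 6.4% to 16.7%.

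**4. Judging on the point value.** When true A_RMS equals the limit, simulation over the same grid at 20 subjects puts the unadjusted point value below the limit 52 to 55% of the time. With one possible variance-component adjustment it is 47 to 50%. As a separate check, with zero bias and effective sample size n, P(χ²ₙ ≤ n) is 0.542, 0.527 and 0.513 for n = 20, 50 and 200.

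**5. Judging on an upper bound.** This uses a one-sided 95% bound from bootstrap-t over subjects on log A_RMS (1,500 runs, 599 resamples). Only the ratio of true A_RMS to the limit matters. A limit of 3 was used for illustration and is not from the documents.

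| True A_RMS / limit | Subjects | Pass on point value | Pass on upper bound |
|---|---|---|---|
| 3.0/3 = 1.00 | 20 | 52–54% | 6.2–8.5% |
| 2.6/3 = 0.87 | 20 | 90.5–99.9% | 28.9–75.5% |
| 2.6/3 = 0.87 | 40 | 95.8–100% | 45.3–94.6% |
| 2.2/3 = 0.73 | 20 | 99.8–100% | 67.9–98.1% |

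At the limit, a t interval on log A_RMS passed 7.4 to 11.4% and a percentile bootstrap 10.2 to 15.2% (800 runs, 10 and 40 pairs). All three exceed the nominal 5%; bootstrap-t exceeds it least.

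**The case against.** The strongest reply is that the equivalence sentence only names the metric. It sits under the outcome measure, the sentence before it speaks of performance, and the objectives, endpoints and 10.1.3 are all descriptive. No hypothesis or alpha appears. This stands in part. A reader might infer that a formal equivalence test is planned and will be run wrongly, and the documents do not show that. They show equivalence language in two places that the analysis section cannot back.

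A second reply is that ISO 80601-2-61 supplies the limit. A reader might conversely infer that no limit exists. Neither can be settled from the documents. What they support is that the plan quotes no limit and does not say A_RMS will be judged against one. If that was intended, a sentence would settle it, worded for differences from RD SET Adt because the reference here is another pulse oximeter.

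Third, the pass rate of about one half is a property of nearly any point estimate at any sample size, and it shifts by a few points with the adjustment chosen. That is correct. It shows why a bare point value cannot carry a determination; it is not a special failing of this design. Nor does the plan overlook clustering: 10.1.3 commits to an adjustment and leaves its method unnamed.

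A last temptation is to say the watch comparison is biased because the W1 reads continuously and the Apple Watch is spot-checked. The documents do not support this. Figure 4 and the text of 8.4.1.2 are not shown, and any size would rest on invented error SDs and no-read rates. Side-by-side A_RMS values can also meet the secondary objective, to "Compare the performance of Masimo W1™ and Apple Watch Series 8 against FDA-cleared hospital grade pulse oximetry technology".

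**Conclusion.** The point holds as a mismatch between 7.1 and 5.1 on one side and section 10 on the other: an equivalence conclusion is announced and only description is planned. Confidence in this is high, because it rests on the text alone.

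The size rests on assumptions about pairs per subject, intraclass correlation and mean bias, none of which the documents give. Under them, A_RMS at 20 subjects varies about 8 to 25% either side of truth (about 6 to 17% at 40). A reader might infer that equivalence will be wrongly declared, but the documents do not show that. They leave it open, and closing it before data are seen is cheap. It should be fixed.

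The absence of a paired W1–Apple estimate is a smaller, optional and less certain matter.

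**What to change.** 1. In 7.1, choose one route.
   - Descriptive: *SpO2 performance against RD SET Adt will be described by bias, precision and A_RMS with subject-clustered 95% CIs; no equivalence claim will be made.* Bring 5.1 into line.
   - Equivalence: state the sponsor's A_RMS limit and its source, for differences from RD SET Adt, before data are seen. Declare equivalence only if the subject-clustered one-sided 95% upper bound of A_RMS is below it.
2. In 10.1.3, name the repeated-measures method and add subject-clustered 95% CIs for bias, precision and A_RMS. Use a method whose coverage at 20 subjects has been checked. Bootstrap-t is slightly liberal here (about 6 to 9% at nominal 5%).
3. Optional: since every subject receives both watches, report the paired W1–Apple difference or ratio of A_RMS with a subject-clustered CI. Any restriction to times with valid Apple readings belongs in a supporting analysis beside the planned No Read Rate, because it conditions on the Apple Watch having read.

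Cost: wording and analysis code, with no new data. The descriptive route costs nothing more. Keeping a limit makes success harder: a device at 0.87 of the limit would pass 29 to 76% of the time at 20 subjects, instead of 91 to 100% on the point value.
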